8.3.2 Pharmacokinetics and Pharmacodynamics Data

The plasma xisomab 3G3 PK profiles were best characterized at the 5 mg/kg dose level. The PK profiles and PK parameters in the 0.1 mg/kg dose level were not well characterized since the majority of concentrations fell below the LLOQ; thus, an insufficient number of time points were available to characterize the elimination phase from 3 out of 4 subjects at that dose level. Terminal phase PK may have not been reliable at the doses below 5 mg/kg, noting that Vss appeared to be underestimated (were less than physiological blood volumes), and that half-life estimations increased when xisomab 3G3 was quantifiable for longer intervals.

Plasma xisomab 3G3 exposure (AUCs and Cmax) increased with increasing dose levels. Although a dose proportionality analysis was not performed in this study, the mean PK parameter values indicated that plasma xisomab 3G3 exposure appeared to increase in a slightly more than dose-proportional manner from 0.5 to 5 mg/kg. The PK parameters calculated from the 0.1 mg/kg dose were less robust as most parameters were estimated in only 1 subject due to the absence of an observable elimination phase in 3 out of 4 subjects. The maximal concentrations peaked early, with Tmax values achieved before 1 hour following start of infusion. Elimination of the drug was decreased with increasing xisomab 3G3 doses, as shown by a lower Kel, longer t_{1/2}, and lower CL. A summary of mean PK parameters and mean concentration profile can be found in [Table 1](#) and [Figure 1](#).

[figure not shown]
Table 1: Key PK Parameters

| Parameters (units) | Dose | | | |
|-------------------------|-------------|--------------|----------------|-----------------|
| | 0.1 mg/kg | 0.5 mg/kg | 2 mg/kg | 5 mg/kg |
| N | 3* | 4 | 4 | 4 |
| AUC0-t (ng•h/mL) | 60.47 ± 38 | 368 500 ± 23 | 5 657 000 ± 24 | 28 270 000 ± 12 |
| AUC0-inf (ng•h/mL) | - | 370 400 ± 23 | 5 668 000 ± 24 | 28 290 000 ± 12 |
| Cmax (ng/mL) | 124.9 ± 23 | 11 250 ± 9 | 42 750 ± 12 | 127 300 ± 3 |
| Tmax (h) | 0.084 ± 2.4 | 1.15 ± 113 | 0.13 ± 65 | 1.01 ± 132 |
| t _{1/2} (h) | - | 16.638 ± 9 | 60.63 ± 7 | 121.49 ± 85 |
| CL (L/h) | - | 0.09 ± 20 | 0.026 ± 13 | 0.014 ± 23 |
| V _{ss} (L) | - | 2.52 ± 24 | 3.72 ± 11 | 4.31 ± 18 |

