13.7.2 Plasma Pharmacokinetic Parameters

The following PK parameters will be computed, as appropriate, for plasma free xisomab 3G3 from the individual plasma concentrations using a non-compartmental approach:

AUC0-t: The area under the plasma concentration-time curve, from time 0 to the last measurable non-zero concentration, as calculated by the linear trapezoidal method.

AUC0-inf: The area under the plasma concentration-time curve from time 0 extrapolated to infinity. AUC0-inf is calculated as the sum of AUC0-t plus the ratio of the last measurable plasma concentration to the elimination rate constant.

AUC%extrap: Percent of AUC0-inf extrapolated, represented as $(1 - AUC0-t/AUC0-inf) * 100$.

Cmax: Maximum observed concentration.

Tmax: Time to reach Cmax. If the maximum value occurs at more than one time point, Tmax is defined as the first time point with this value.

Kel: Apparent first-order terminal elimination rate constant calculated from a semi-log plot of the plasma concentration versus time curve. The parameter will be calculated by linear least-squares regression analysis using the maximum number of points in the terminal log-linear phase (e.g., three or more non-zero plasma concentrations).

t½: Apparent first-order terminal elimination half-life will be calculated as 0.693/kel.

CL: Apparent total plasma clearance calculated as Dose/AUC0-inf.

Vss: Total apparent volume of distribution following single IV dose administration calculated as $V_{ss} = MRT \times CL$.

MRT*: Mean residence time = $AUMC_{0-\infty}/AUC_{0-\infty}$ (for IV infusion)

AUMC_{0-∞}*: Area under the moment curve from time 0 to the last measurable concentration, = $AUMC_{0-t} + [(t_{last} \times C_t)/\text{Kel}] + C_t/(\text{Kel})^2$

* AUMC_{0-∞} and MRT values will be used for Vss calculation but will not be listed in the PK tables.

Additional PK parameters may be computed if deemed appropriate.

Plasma concentrations below the limit of quantitation will be treated as missing for all PK calculations.

No PK parameters will be calculated for patients with 2 or fewer consecutive time points with detectable concentrations.

No value for Kel, t½, AUC0-inf, AUC%extrap, CL, and Vss, as appropriate, will be reported for cases that do not exhibit a terminal log-linear phase in the concentration-time profile.

Individual and mean plasma concentration time curves (both linear and log-linear) will be included in the final report.

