### **6.2 Bioanalytical Method**

Plasma concentrations of xisomab 3G3 will be determined using enzyme-linked immunosorbent assay (ELISA) validated with respect to accuracy, precision,

linearity, sensitivity, and specificity at Celerion, Lincoln, Nebraska. The analytical range (lower limit of quantitation [LLOQ] – upper limit of quantitation [ULOQ]) for xisomab 3G3 is expected to be 50 – 5000 ng/mL.

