**Table 6.1. Noncompartmental Pharmacokinetic Parameters to be Calculated**

Parameter Label to be Used in the Text, Tables and Figures	Definition	Method of Determination
AUC0-t	Area under the concentration-time curve from time 0 to the time of the last measurable non-zero concentration	Calculated using the Linear Trapezoidal with Linear Interpolation Method
AUC0-inf	Area under the concentration-time curve from time 0 extrapolated to infinity	$AUC0-inf = AUC0-t + (C_{last}/k_{el})$ where $C_{last}$ is the last observed/measured concentration
AUC%extrap	Percent of AUC0-inf extrapolated	$AUC\%extrap = (1 - AUC0-t/AUC0-inf) * 100$
AUMC0-inf*	Area under the moment curve from time 0 extrapolated to infinity	$AUMC0-inf = AUMC0-t + [(t_{last} \times C_{last}) / k_{el}] + [C_{last} / (k_{el})^2]$
Cmax	The maximum observed concentration	Taken directly from bioanalytical data
Tmax	The time to reach Cmax. If the maximum value occurs at more than one time point, Tmax is defined as the first time point with this value	Taken from clinical database as the difference in the start time of the infusion and the time of the blood draw which is associated with the Cmax.
Kel	Apparent first-order terminal elimination rate constant calculated from a semi-log plot of the plasma concentration versus time curve	The parameter will be calculated by linear least-squares regression analysis using the maximum number of points in the terminal log-linear phase (e.g., three or more non-zero plasma concentrations).
t 1/2	Apparent first-order terminal elimination half-life	Calculated as: $0.693 / k_{el}$
CL	The apparent total plasma clearance after IV administration	Calculated as: $Dose / (AUC0-inf)$
MRT*	Mean residence time of free drug in the systemic circulation when the drug concentrations are extrapolated to infinity	Calculated as: $(AUMC0-inf / AUC0-inf) - (T_{1/2})$ Where TI is the duration of infusion
Vss	Total apparent volume of distribution following single IV dose administration	Calculated as: $MRT \times CL$

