\* AUMC0-inf and MRT values will be used for Vss calculation but will not be listed in the PK tables. Note for the programmer: Parameters which are calculated for use in the calculation of a separate parameter but that are not summarized in the PK tables (i.e., AUMC0-inf and MRT) will be included in the study data tabulation model (SDTM) PP(Pharmacokinetic Parameters) domain, but not included in the analysis data model (ADaM) ADPP (Pharmacokinetic Parameters Analysis) domain.

PK parameters will not be calculated for patients with 2 or fewer consecutive time points with detectable concentrations. Subjects for whom there are insufficient data to calculate the PK parameters will be included in the concentration tables only and excluded from the summary statistics.

For the calculation of the PK parameters, plasma concentrations below the limit of quantitation (BLQ) prior to the first quantifiable concentration will be set to 0 and plasma concentrations BLQ after the first quantifiable concentration will be treated as missing.

The Kel will be determined using linear regressions composed of least 3 data points. The Kel will not be assigned if 1) the terminal elimination phase is not apparent, 2) if Tmax is one of the 3 last data points, or 3) if the R^2 value is less than 0.75. In cases where the Kel interval is not assigned, the values of AUC0-inf, AUC%extrap, AUMC0-inf, t1/2, CL, MRT, and Vss are considered not calculable and will not be reported. Wherever the resulting t1/2 is more than half as long as the sampling interval, the Kel values and associated parameters (AUC0-inf, AUC%extrap, AUMC0-inf, t1/2, CL, MRT, and Vss) may not be presented as judged appropriate and in accordance with Celerion SOPs.

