## 6.6 Data Summarization and Presentation of PK Parameters

All plasma xisomab 3G3 PK concentrations and/or PK parameters descriptive statistics will be generated using SAS® version 9.3 or higher. A concentration table will be presented for pooled placebo samples without descriptive statistics.

The plasma concentrations of xisomab 3G3 will be listed and summarized by treatment and time points for all subjects in the PK population. Plasma concentrations of xisomab 3G3 will be presented with the same level of precision as received from the bioanalytical laboratory. Summary statistics, including sample size (n), arithmetic mean (Mean), standard deviation (SD), coefficient of variation (CV%), standard error of the mean (SEM), minimum, median, and maximum will be calculated for all nominal concentration time points. Excluded subjects will be included in the concentration listings, but will be excluded from the summary statistics and noted as such in the tables. All BLQ values will be presented as “BLQ” in the concentration listings and footnoted accordingly.

Mean and individual concentration-time profiles will be presented on linear and semi-log scales. Linear mean plots will be presented with and without SD.

Plasma xisomab 3G3 PK parameters will be listed and summarized by treatment for all subjects in the PK population. Pharmacokinetic parameters will be reported to 3 significant figures for individual parameters, with the exception of  $t_{1/2}$  and  $T_{max}$ , which will be presented with 2 decimal places. Summary statistics (n, Mean, SD, CV%, SEM, minimum, median, maximum, geometric mean [Geom Mean] and geometric CV% [Geom CV%]) will be calculated for plasma xisomab 3G3 PK parameters. Excluded subjects will be listed in the PK parameter tables, but will be excluded from the summary statistics and noted as such in the tables.

The level of precision for each concentration and PK parameter statistic will be presented as follows:

- minimum/maximum: in same precision as in the bioanalytical data for concentrations and same precision for PK parameters presentation
- Mean/median/Geom Mean: in one more level of precision than minimum/maximum
- SD/SEM: in one more level of precision than Mean/median/Geom Mean
- n will be presented as an integer
- CV% and Geom CV% will be presented to the nearest tenth

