For the calculation of summary statistics, values that are below the limit of quantitation (BLQ) of <X> ng/mL are treated as 0 before the first quantifiable concentration and as missing elsewhere.

. = Value missing or not reportable.

---

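### Late mean and median drug concentrations will describe only patients still above the assay limit, so they overstate late levels and flatten the tail of the semi-log mean plot

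*SAP*

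**What the plan says.** The rule for summary statistics is in the footnote to the shell for Table 14.2.1.1.1 (SAP 11.3): BLQ values "are treated as 0 before the first quantifiable concentration and as missing elsewhere". The limit is left as a placeholder there. SAP 6.2 says that the analytical range "for xisomab 3G3 is expected to be 50 – 5000 ng/mL".

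SAP 6.6 requires n, mean, SD, CV%, SEM and then "minimum, median, and maximum will be calculated for all nominal concentration time points". Nothing in SAP 6.6, the shells or the figure notes withholds or flags a mean when few values are quantifiable. SAP 6.1 and the shell notes put the late samples at 48, 96, 120, 144 and 192 h.

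Individual values remain visible: "All BLQ values will be presented as “BLQ” in the concentration listings and footnoted accordingly".

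PK parameters have their own rule, applied within each patient. In the SAP, "plasma concentrations BLQ after the first quantifiable concentration will be treated as missing". Protocol 13.7.2 agrees for these late values: "Plasma concentrations below the limit of quantitation will be treated as missing for all PK calculations". AUC0-t is the "Area under the concentration-time curve from time 0 to the time of the last measurable non-zero concentration".

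**The concern.** As drug disappears, the rule removes the lowest values from each late summary and keeps the highest. The mean, median and minimum become conditional on being above the LLOQ, and the denominator shrinks without any change in the label.

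This is likely to happen in this trial. In the first-in-human study at 0.1 mg/kg, "the majority of concentrations fell below the LLOQ" (Protocol 8.3.2), and the lower dose here is 0.25 mg/kg. With 9 to 12 patients per cohort at 2:1, each dose has 6 to 8 active patients, so a late plotted mean may rest on one or two of them.

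At stake are the late columns of Tables 14.2.1.1.1 and 14.2.1.1.2 and the tail of the semi-log mean plot, Figure 14.2.1.2.3. That tail is where a reader judges how fast the drug is eliminated. The figure notes in SAP 11.2 do not ask for n, so the plot does not show that the denominator has shrunk.

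**Working it through.** The plan gives no figure of its own to reproduce, so the check asks when values become BLQ and how far the planned mean then departs from the true mean.

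**Inputs.** LLOQ 50 ng/mL (SAP 6.2, expected). At 0.5 mg/kg, Cmax 11,250 ng/mL and half-life 16.638 h, each with CV 9% (Protocol Table 1). Late times from SAP 6.1. There are no first-in-human data at 0.25 mg/kg, so its inputs are assumed: starting concentration 2,000 to 5,625 ng/mL (the upper value is half of 11,250) and half-life 10 to 16.6 h.

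**Step 1: when 0.5 mg/kg crosses the LLOQ.** With mono-exponential decline, t = half-life × log2(Cmax/LLOQ) = 16.638 × log2(11,250/50) = 16.638 × 7.814 = 130 h. Expected concentrations are about 76, 28 and 4 ng/mL at 120, 144 and 192 h.

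*Sensitivity to shape.* This model gives an AUC of 11,250 × 16.638/0.693 ≈ 270,000 ng·h/mL, against 370,400 in Table 1, so the real profile falls more slowly somewhere. If the gap were an initial flat stretch at Cmax, it would last (370,400 − 270,100)/11,250 = 8.9 h and move the crossing to about 139 h, still before 144 h.

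*Sensitivity to half-life.* The crossing reaches 144 h at a half-life of 144/7.814 = 18.4 h, and 192 h at 192/7.814 = 24.6 h.

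**Step 2: when 0.25 mg/kg crosses.** 16.638 × log2(5,625/50) = 113 h; 10 × log2(5,625/50) = 68 h; 10 × log2(2,000/50) = 53 h.

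**Step 3: overstatement, by formula.** For log-normal concentrations with log-scale SD s = √ln(1 + CV²), the mean of quantifiable values over the true mean is Φ(s − a)/(1 − Φ(a)), where a = ln(LLOQ/median)/s.

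| CV | s | 20% BLQ (a = −0.842) | 50% BLQ (a = 0) | true median half the LLOQ |
|---|---|---|---|---|
| 25% | 0.246 | 1.08 | 1.19 | 2.09 |
| 50% | 0.472 | 1.13 | 1.36 | 2.25 |

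**Step 4: overstatement, by simulation.** Cohorts of 8 active patients, mono-exponential decline, log-normal starting concentration and half-life. Means are in ng/mL, averaged over cohorts with at least one quantifiable value.

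| Scenario | Time | BLQ | Cohorts with a mean | Planned mean | True mean | Ratio |
|---|---|---|---|---|---|---|
| 0.5 mg/kg, both CVs 9% | 120 h | 20% | 100% | 91 | 80 | 1.13 |
| same | 144 h | 88% | 64% | 65 | 33 | 1.94 |
| 0.5 mg/kg, half-life CV 30% | 120 h | 45% | 100% | 205 | 122 | 1.69 |
| same | 144 h | 69% | 95% | 153 | 60 | 2.57 |
| same | 192 h | 93% | 44% | 109 | 23 | 4.73 |
| 0.25 mg/kg, 5,625 and 16.6 h, CVs 9% | 120 h | 75% | 90% | 66 | 41 | 1.59 |
| 0.25 mg/kg, 5,625 and 10 h, CVs 20% and 30% | 96 h | 91% | 54% | 102 | 25 | 4.07 |

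The smallest planned mean in any simulated cohort was 50.0 ng/mL.

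**Step 5: effect on apparent slope.** In the first scenario the planned mean goes from 91 to 65 between 120 and 144 h, an apparent half-life of 24 × 0.693/ln(91/65) ≈ 49 h. The true means, 80 to 33, give 24 × 0.693/ln(80/33) ≈ 19 h.

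**Step 6: the median.** Take 8 patients, 3 quantifiable at 120, 80 and 60. The planned mean is 86.7 and the planned median 80. Ranking the five BLQ values below the LLOQ puts the median at BLQ. Substituting 0 gives a mean of 32.5, and substituting LLOQ/2 gives (260 + 5 × 25)/8 = 48.1.

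**Step 7: PK parameters.** These come from individual profiles, and AUC0-t stops at each patient's last measurable value, so late BLQ values do not enter it. Even the area under the planned mean curve was 0.97 to 1.03 times that of the true mean curve.

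**The case against.** The strongest reply is that this concerns presentation in the tail and that much is already disclosed. The tables print n and every patient's value, the footnote states the rule, the listings mark BLQ, and individual profiles are plotted on both scales. That stands for the tables. It does not help someone reading the mean plot, and n alone does not separate BLQ from missed samples.

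Some stronger readings are tempting but not supported:

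- **That exposure is overstated.** The protocol uses exposure for AUCs and Cmax, which are derived patient by patient and do not inherit this bias.
- **That Figure 11-1 will show a false plateau.** It is a linear plot of both doses. The 144 h gap at 0.5 mg/kg is 65 − 33 = 32 ng/mL, about 0.3% of 11,250, and could not be seen. The simulated planned mean also still falls.
- **That a doubling will be routine.** When the true median is half the LLOQ, 0.24% of values are quantifiable at CV 25% and 7% at CV 50%. With 6 to 8 patients, a mean then exists in only about 2% and in 36% to 45% of cohorts.
- **That 50 ng/mL is a fixed floor.** It is an expected limit, and a BLQ value before a patient's first quantifiable one counts as 0, though that is unlikely to matter late after an IV dose.
- **That a formal dose comparison is compromised.** The SAP plans no dose-proportionality test or PK/PD model.

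The timing also rests on weak inputs: Protocol 8.3.2 warns that terminal-phase estimates below 5 mg/kg may be unreliable. Finally, substitution has its own bias: with BLQ set to 0, the 144 h mean in the first scenario is 12 against a true 33.

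**Conclusion.** The point holds as a bias in late summary concentrations. It is a stated rule with a predictable direction. Late means and medians describe only patients above the LLOQ and effectively cannot go below it. The mean is overstated about 1.1 to 1.4 times at 20% to 50% BLQ with moderate spread, and up to 1.7 times at 45% BLQ if half-lives have a CV of 30%. Where 69% to 93% are BLQ and a mean still prints, it is about 1.6 to 4.7 times too high, typically 2 or more.

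At 0.5 mg/kg the 144 and 192 h samples are likely to be affected. This rests on an LLOQ of 50 ng/mL, first-in-human values from healthy subjects, and roughly mono-exponential decline. At 0.25 mg/kg the effect probably comes earlier, but that depends on assumed inputs. Direction and approximate size are reliable; exact factors are not.

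The consequence is confined to the late table columns and the tail of Figure 14.2.1.2.3, where elimination looks slower than it is. No individual PK parameter changes. This is a cheap improvement, not a threat to the trial's conclusions.

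**What to change.** Change SAP 6.6 and the concentration-table shells, for concentration summaries and mean plots only:

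- Show n sampled and n BLQ at each nominal time.
- Report the median with BLQ values ranked below the LLOQ, shown as BLQ if it falls there. State the convention for an even number of patients when one of the two middle values is BLQ.
- Do not print or plot a mean where more than half the values are BLQ.

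Leave the rule for individual PK parameters unchanged.

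The cost is a few lines of SAP wording and one added table row, with no new data. The downside is that the mean curve stops earlier. Means with up to half the values BLQ would still print and keep the smaller bias, but the BLQ count would then disclose it. Fixing the cut-off before unblinding also avoids choosing where the curve stops after seeing the data.

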**Notes for Generating the Actual Table:**

- Please use CPConcl template
- Per study design needs, the following changes are made to this table relative to Celerion standard: columns <Treatment Sequence> and <Study Period> will be removed.
- Concentrations will be presented to the same precision as in the bio data.
- aPTT values will be presented to the same precision as in the clinical laboratory data.
- Summary statistics presentation with respect to the precision of the bio data or clinical laboratory data: n = integer; Mean and Median +1; SD and SEM +2, Minimum and Maximum +0, CV% to 1 decimal
- PK Time points are: predose (hour 0) and 0.167, 0.5, 1, 2, 3, 4, 6, 8, 12, 16, 24, 48, 96, 120, 144, and 192 hours postdose (additional time points might be added depending on the conduct of the study)
- For Tables 14.2.5.1.1 through 14.2.5.1.3, aPTT values will be reported during the course of the study from Days -7 through 12 with adding "Day" above the "Sampling Time".
- For Tables 14.2.5.1.3 and 14.2.5.1.6, there will be no summary statistics

Program: /CAXXXX/sas\_prg/pksas/pk-conc-tables.sas DDMMYYYY HH:MM  
Program: /CAXXXX/sas\_prg/pksas/pk-conc-tables-sig.sas DDMMYYYY HH:MM  
Program: /CAXXXX/sas\_prg/pksas/adam\_conc.sas DDMMYYYY HH:MM

Tables 14.2.1.1.4 and 14.2.1.1.5 will be in the following format:

Table 14.2.1.1.4 Plasma Xisomab 3G3 Pharmacokinetic Parameters Following a Single IV Infusion of 0.25 mg/kg Xisomab 3G3 (Pharmacokinetic Population)

Subject Number	Parameters					
	param1 (units)	param2 (units)	param3 (units)	param4 (units)	param5 (units)	param6 (units)
X	XXX	X.XX	XXX	XXX	XX.X	X.XXX
X	XX.X	X.XX	XXX	XXX	XX.X	X.XXX
X	XXX	X.XX	XXX	XXX	XX.X	X.XXX
X	XX.X	X.XX	XXX	XXX	XX.X	X.XXX
X	XX.X	X.XX	XXX	XXX	XX.X	X.XXX
X	X.XX	X.XX	XXX	XXX	XX.X	X.XXX
X	XXX	X.XX	XXX	XXX	XX.X	X.XXX
n	XX	XX	XX	XX	XX	XX
Mean	XXX.X	X.XXX	XXX.X	XXX.X	XX.XX	X.XXXX
SD	XX.XX	XX.XX	XX.XX	XX.XX	XX.XX	XX.XX
CV%	XX.X	XX.X	XX.X	XX.X	XX.X	XX.X
SEM	XX.XX	XX.XX	XX.XX	XX.XX	XX.XX	XX.XX
Minimum	XX.X	X.XX	XXX	XXX	XX.X	X.XXX
Median	XX.XX	X.XXX	XXX.X	XXX.X	XX.XX	X.XXXX
Maximum	XXX	X.XX	XXX	XXX	XX.X	X.XXX
Geom Mean	XXX.X	X.XXX	XXX.X	XXX.X	XX.XX	X.XXXX
Geom CV%	XX.X	XX.X	XX.X	XX.X	XX.X	XX.X

. = Value missing or not reportable.

---

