8.4.2 Rationale for the Dose Selection

Doses of 0.25 mg/kg and 0.5 mg/kg were selected for this phase 2 study in order to provide adequate PD and PK characterization but still allowing a safety margin should the results differ in this population compared to healthy subjects. The 0.25 mg/kg xisomab 3G3 dose is 2.5-fold higher than the lowest dose in the FIH study. The 0.1 mg/kg dose in the FIH study had a short and modest, yet detectable PD effect (several seconds of temporal aPTT prolongation). The 0.25 mg/kg dose is expected to provide an initial plasma concentration that is within the range of average FXI concentration, the molecular target of xisomab 3G3, in human subjects, and may approach saturation in some individuals after full distribution. Therefore, it has the potential to exert brief pharmacological (anti-inflammatory, antithrombotic) activity, possibly lasting up to a day, until elimination of the antibody and hepatic FXI secretion that neutralizes the antibody.

The 0.5 mg/kg dose was safely administered in the FIH study and allowed adequate characterization of the PK profile in healthy adults. In addition, following a 0.5 mg/kg a prolongation of aPTT was seen, with highest values measured at 24 hours postdose and having a sustained effect for at least 72 hours postdose. The 0.5 mg/kg xisomab 3G3 dose is expected to provide, after complete distribution, a plasma concentration that is approximately twice the average human plasma concentration of the FXI antigen. Therefore, this dose is expected to be overcome by FXI generation later, and have pharmacological activity that lasts longer than the lower dose level.

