14.3.3 Pharmacodynamic Analyses

Placebo patients from Cohort 1 and Cohort 2 will be pooled for analysis.

The PD analysis will include assessments of drug potency and efficiency of HD. These will include change in aPTT, BUN, and potassium levels. Change in thrombus accumulation, in total dialysate urea, URR, and Kt/V after xisomab 3G3 levels versus pre-treatment and placebo will also be evaluated. Total protein accumulation within HD filter will be evaluated.

The change from baseline in PD endpoints will be summarized by treatment (2 active dose levels and pooled placebo) and at each scheduled time point using descriptive statistics. The baseline values are any value observed from Day -7 to Day 1, prior to xisomab 3G3 administration. Any values after a single dose of xisomab 3G3 are regarded as post baseline values.

The change from baseline variables will be calculated as the post-baseline value minus the value at baseline.

Additional analyses may be performed as deemed necessary upon review of the data.

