## 7.2 Data Summarization and Presentation of PD Parameters

### 7.2.1 aPTT

**Sample Collection:** Samples for the coagulation parameter (aPTT) will be collected at screening, pre- and post-dialysis on Days -7, -5, -3, 1, 3, 5, and 12. Additional samples for aPTT will be collected following xisomab 3G3/placebo dosing on Day 1 at predose (hour 0, at least 1 hour prior the start of HD session) and at 0.167, 0.5, 1, 2, 3, 4, 6, 8, 12, 16, 24, 48, 96, 120, 144, and 192, hours after xisomab 3G3 start of infusion.

**Baseline Calculation Method Following Day 1 Dosing:** Following xisomab 3G3 dosing on Day 1, aPTT change from baseline will be calculated by dividing postdose aPTT values from average of pre-dose baseline (the average of pre-dialysis aPTT values on Days -7, -5, -3, and 1 will be calculated as pre-dose baseline).

**Fold change in aPTT values:** The fold change in aPTT values on Days -7, -5, -3, 1 (only pre- and post-dialysis aPTT values on Day 1), 3, 5, and 12 will be calculated by dividing the post-dialysis aPTT/pre-dialysis aPTT values for each day separately.

aPTT values will be extracted from the clinical laboratory database and descriptive statistics will be generated using SAS® version 9.3 or higher. Following Day 1 xisomab 3G3 dosing, a table will be presented for the aPTT change from baseline with descriptive statistics.

aPTT values will be listed and summarized by treatment and time points in Tables and Figures for all subjects in the Safety Population (2 active dose levels and pooled placebo). aPTT values will be presented with the same level of precision as received from the clinical laboratory database. Summary statistics, including n, Mean, SD, CV%, SEM, minimum, median, and maximum will be calculated for all nominal values time points. Excluded subjects will be included in the aPPT values tables, but will be excluded from the summary statistics and noted as such in the tables.

Mean and individual aPTT values-time and change from baseline-time profiles will be presented on linear scale. Linear mean plots will be presented with and without SD.

The level of precision for the aPPT values summary statistic will be presented as follows:

- minimum/maximum: in same precision as in the clinical laboratory database
- Mean/median: in one more level of precision than minimum/maximum
- SD/SEM: in one more level of precision than Mean/median
- n will be presented as an integer
- CV% will be presented to the nearest tenth

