### 14.2.5 aPTT Tables and Figures

Table 14.2.5.1.1 Individual and Mean aPTT Values (unit) During the Course of the Study (Days -7 to 12) and Following a Single IV

	Infusion of 0.25 mg/kg Xisomab 3G3 on Day 1 (Safety Population)
Table 14.2.5.1.2	Individual and Mean aPTT Values (unit) During the Course of the Study (Days -7 to 12) and Following a Single IV Infusion of 0.5 mg/kg Xisomab 3G3 on Day 1 (Safety Population)
Table 14.2.5.1.3	Individual and Mean aPTT Values (unit) During the Course of the Study (Days -7 to 12) and Following a Single IV Infusion of Placebo (Pooled) on Day 1 (Safety Population)
Table 14.2.5.1.4	Individual and Mean aPTT Change From Baseline Values (unit) Following a Single IV Infusion of 0.25 mg/kg Xisomab 3G3 on Day 1 (Safety Population)
Table 14.2.5.1.5	Individual and Mean aPTT Change From Baseline Values (unit) Following a Single IV Infusion of 0.5 mg/kg Xisomab 3G3 on Day 1 (Safety Population)
Table 14.2.5.1.6	Individual and Mean aPTT Change From Baseline Values (unit) Following a Single IV Infusion of Placebo (Pooled) – Day 1 (Safety Population)

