**Programmer Note:**

***For Tables 14.2.5.1.4 through 14.2.5.1.6, aPTT baseline will be the average of all pre-dialysis aPTT value on Days -7, -5, -3 and 1, and the change from baseline will be calculated as follows: (post-dialysis/baseline).***

Table 14.2.5.1.7	Individual and Mean Difference Between Pre- and Post-dialysis aPTT Values (unit) – Days -7 to 12 – 0.25 mg/kg Xisomab 3G3 on Day 1 (Safety Population)
Table 14.2.5.1.8	Individual and Mean Difference Between Pre- and Post-dialysis aPTT Values (unit) – Days -7 to 12 – 0.5 mg/kg Xisomab 3G3 on Day 1 (Safety Population)
Table 14.2.5.1.9	Individual and Mean Difference Between Pre- and Post-dialysis aPTT Values (unit) – Days -7 to 12 – Placebo (Pooled) (Safety Population)

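### SAP shell notes remove summary statistics from the two pooled-placebo aPTT tables, and a postdose-to-baseline aPTT ratio is presented as a change in seconds

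*SAP*

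**What the plan says.** **Placebo statistics.** The notes to the shared shell for Tables 14.2.1.1.1–3 and 14.2.5.1.1–6 (SAP 11.3) say: "For Tables 14.2.5.1.3 and 14.2.5.1.6, there will be no summary statistics". The table list in SAP 10.2 shows that Table 14.2.5.1.3 holds the pooled-placebo aPTT values and Table 14.2.5.1.6 the pooled-placebo change from baseline. The second is titled "Individual and Mean aPTT Change From Baseline Values (unit) Following a Single IV Infusion of Placebo (Pooled"), and the first title also promises individual and mean values. SAP 7.2.1 says "aPTT values will be listed and summarized by treatment and time points in Tables and Figures", names pooled placebo as one of the groups, and lists n, mean, SD, CV%, SEM, minimum, median and maximum. Protocol 14.3.3 has the change from baseline in PD endpoints summarised by treatment, namely "2 active dose levels and pooled placebo) and at each scheduled time point using descriptive statistics". Elsewhere, the SAP withholds placebo statistics explicitly only for drug concentrations, in Section 6.6: "A concentration table will be presented for pooled placebo samples without descriptive statistics".

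**Ratio or difference.** SAP 7.2.1 says "aPTT change from baseline will be calculated by dividing postdose aPTT values from average of pre-dose baseline". The programmer note for Tables 14.2.5.1.4–6 says "the change from baseline will be calculated as follows: (post-dialysis/baseline"). The axis specification for Figures 11-6, 14.2.5.2.5 and 14.2.5.2.6 (SAP 11.2) gives this quantity in seconds. Protocol 14.3.3 defines change from baseline as the later value minus the baseline value. SAP Section 9 lists only the dialysis length and the BUN/potassium sampling time as changes, and otherwise declares agreement with the protocol.

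**The concern.** SAP 2.2 defines the PD endpoint as a comparison with both pre-treatment and placebo. Protocol 8.4.2 describes aPTT after 0.5 mg/kg in the first-in-human study "with highest values measured at 24 hours postdose and having a sustained effect for at least 72 hours postdose", and expects activity after 0.25 mg/kg to last possibly up to a day. The first 24 hours are therefore the window that matters most. Under the shell note, the tables at 24 hours would give n, mean and SD for each dose and none for placebo.

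The labelling problem affects all three groups. A ratio of two clotting times has no unit and a null value of 1. Plotted on an axis marked as a change in seconds, a group with no effect would look as if aPTT had lengthened by one second.

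**Working it through.** There is no plan figure to reproduce, since the sample size is not based on a calculation (protocol 14.1). The check compares the instructions and counts time points.

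**1. Where the shells and the text disagree**

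| Table | Content | Text requires | Shell note gives |
|---|---|---|---|
| 14.2.5.1.3 | Placebo aPTT values | Statistics (SAP 7.2.1, title) | None |
| 14.2.5.1.6 | Placebo aPTT change from baseline | Statistics (protocol 14.3.3, SAP 7.2.1, title) | None |
| 14.2.1.1.3 | Placebo drug concentrations | None (SAP 6.6) | Shared shell with statistics rows, not exempted |

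The shells drop the statistics where they are required and keep them where they are excluded.

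**2. Is the placebo group too small to summarise?** Allocation is 2:1 in cohorts of 9 to 12.
- Placebo per cohort: 9/3 = 3 to 12/3 = 4, so pooled placebo is 6 to 8.
- Each active dose: 9 × 2/3 = 6 to 12 × 2/3 = 8.

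Pooled placebo is as large as each dose group, so size is no reason to omit it.

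**3. Postdose times left without tabulated placebo statistics**
- SAP 7.2.1 lists 0.167, 0.5, 1, 2, 3, 4, 6, 8, 12, 16, 24, 48, 96, 120, 144 and 192 hours: 16 times.
- Tables 11-6 and 14.2.5.1.9 still summarise placebo before and after dialysis. They cover the end of dialysis on Day 1 (3 or 4 hours, one of the two), pre-dialysis on Day 3 (48 hours) and pre-dialysis on Day 5 (96 hours): 3 times. If the 120-hour sample fills the Day 6 row of the shell, the count is 4.
- Missing: 16 − 3 = 13 (81%) or 16 − 4 = 12 (75%).
- Up to 24 hours there are 11 times and 1 is covered, so 10 are missing. All five times from 6 to 24 hours (6, 8, 12, 16, 24) are missing.
- Tables 11-6 and 14.2.5.1.9 compare post- with pre-dialysis on the same day. They do not summarise placebo change from the predose baseline.

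**4. Ratio against difference.** Let B be the baseline and P the postdose value.
- Protocol: P − B, in seconds, null 0.
- SAP: P/B, no unit, null 1.

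The documents give no aPTT values in readable form, so the following is an illustration under assumed values: baseline 25–40 s, prolongation 25–100%. The difference runs from 25 × 0.25 = 6.25 s to 40 × 1.00 = 40 s. The SAP quantity runs from 1.25 to 2.0 on an axis marked in seconds.

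**5. Numerator.** SAP 7.2.1 uses postdose values, while the programmer note uses post-dialysis values. Taken literally, the note would restrict the calculation to end-of-session samples and would not describe the postdose time course.

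**The case against.** The strongest reply is that the first defect is a numbering slip in one shell note. The SAP body text, the table titles and the protocol all point the other way, and SAP Section 11 says the shells may change and show only general layout. Little is lost in any case. The two tables still list every placebo patient, and Figures 14.2.5.2.2, 14.2.5.2.4 and 14.2.5.2.6 plot placebo means with SD. Table 14.3.5.5 (coagulation) might also pick up the missing times. The count can be challenged too: 144 and 192 hours fall on Days 7 and 9, while the protocol's return visits are Days 8, 10 and 12. On the second defect, the division is stated in words and as a formula, raw aPTT in seconds is reported alongside, and protocol 14.3 lets the SAP modify secondary analyses. aPTT is descriptive and no decision rule depends on it.

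Much of this stands as mitigation. A slip is the likely explanation, the comparator survives in figures and listings, and the SAP was free to adopt a ratio. Without 144 and 192 hours the count becomes 10 to 11 of 14 (71–79%), which leaves the conclusion unchanged. Table 14.3.5.5 is not a clear remedy, because SAP 8.4 sends aPTT results to the PD section. The mean (SD) figures require the same statistics that the tables are told to omit. Programmers still hold contradictory instructions, and the freedom to use a ratio does not excuse leaving it undeclared under a label in seconds. For its other aPTT ratio, in Table 11-6, the SAP does use the term fold change.

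**Conclusion.** Both defects hold and should be corrected before the tables and figures are programmed. As written, 12 to 13 of the 16 postdose times listed in the SAP have no tabulated placebo aPTT statistics, including 10 of the 11 up to 24 hours. The planned tables do not clearly provide a summary of placebo change from the predose baseline anywhere. The count assumes that the Day 1, 3 and 5 dialysis samples serve as the matching nominal times, and the range depends on whether 120 hours fills the Day 6 row. That the note was meant for Table 14.2.1.1.3 is an inference. The ratio's wrong unit and its null of 1 rather than 0 follow from the formulas alone; only the sizes in seconds rest on assumed values. The loss concerns presentation of a secondary PD endpoint. The data and the primary safety analysis are unaffected.

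**What to change.** 1. In the SAP 11.3 notes, delete the bar on statistics for Tables 14.2.5.1.3 and 14.2.5.1.6 and apply it to Table 14.2.1.1.3, in line with SAP 6.6.
2. Choose one definition of aPTT change from baseline:
   - **Option A:** report the protocol's difference in seconds, using the SAP's baseline (mean of the pre-dialysis values on Days -7, -5, -3 and 1). The axis label then stands, and SAP 7.2.1 and the programmer note change to a subtraction.
   - **Option B:** keep the ratio and call it fold of baseline (unitless, null 1). Correct the titles of Tables 14.2.5.1.4–6 and the titles and axes of Figures 11-6, 14.2.5.2.5 and 14.2.5.2.6, and declare the departure in SAP Section 9.
3. Under either option, replace post-dialysis with postdose in the programmer note for Tables 14.2.5.1.4–6.

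The cost is minor SAP wording, shell and programming edits. Option A also changes one derivation. No new data or assessments are needed.
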